**Table 5. RE-AIM Elements and Corresponding Measures**

RE-AIM Elements (Phase 2)	Proposal's Corresponding Measures
Reach: Representativeness of patients who are willing to participate in the intervention	Characteristics of enrolled study participants from a given PACT patient panel compared to those of all PACT patients meeting eligibility criteria from that panel
Effectiveness: Intervention's impact on important outcomes, including negative effects like diabetes distress	Differences in HbA1c and DDS between EPIC and EUC study arms at 4 months (post-intervention)
Adoption: Representativeness of settings & intervention agents willing to initiate a program and their actual use of program or intervention components	
 
1) Characteristics of PACT teams with participating members
 
2) Timing and frequency of one-on-one sessions following each group sessions
 

Implementation: The intervention agents' fidelity to the various elements of an intervention's protocol; patients' use of the intervention strategies; and the costs and cost-effectiveness of the intervention	
 
1) Proportion of group sessions attended (out of six) for each enrolled patient
 
2) Proportion of individual sessions attended (out of six) for each enrolled patient
 
3) Objective ratings of individual session providers' fidelity to the collaborative goal-setting methodology using a structured fidelity rating process completed by a behavioral coaching expert on the study team
 
4) Patients' perceptions of goal-setting engagement by providers in both the intervention and EUC arms
 
5) Objective ratings of goal and action plan quality using our validated GET-D tool by trained research staff blinded to random assignment
 
6) Cost-utilization and cost-effectiveness of EPIC compared with EUC arms.
 

Maintenance: Long-term effects of a program on outcomes 6 or more months after the most recent intervention contact	Differences in HbA1c and DDS between EPIC and EUC study arms to measure intervention persistence at 10 months

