PACTs, 100 patients in each treatment arm (i.e., EPIC and EUC) will allow for 80% power to detect small-to-medium effects and 98% power to detect medium effects ( $d = 0.50$ ). To account for the dependency among patients within a PACT, the Design Effect (Deff) was applied, following the approach of Schnurr et al. The sample size was inflated using the formula,  $Deff = 1 + (n-1)\rho$ , where  $n$  is the average number of patients per PACT and  $\rho$  is the ICC for PACTs. In our preliminary work, we identified an ICC for PACTs of 0.0183, an average of 27 eligible patients per PACT, and expect that an average of 12 patients per PACT will participate, which yields  $Deff = 1 + (12-1) * 0.0183 = 1.2013$ . Applying this adjustment, the minimum number of patients in the clustered design is  $100 \times 1.2013 = 120$  in each treatment group. Further adjusting for a maximum of 15% attrition, 142 patients will be recruited for each treatment group (total  $N = 284$ ). Therefore, the minimum number of PACTs to be sampled for this nested analysis is technically 11.8, (i.e.,  $142/12$ ), which will be rounded up to 24 PACTS. This is highly feasible, representing just 32.5% of the total number of PACTs (75) at all study sites. Treatment group effect sizes as small as  $d = .40$  can be detected with 80% power at 1-year given a total of 284 patients (an average of approximately 12 patients randomized to either EPIC or EUC from within 24 PACTs sampled), even after accounting for maximum attrition and estimated dependency within PACTs. A sample size of 284 participants is adequate for repeated measures analyses as well. Optimal design software estimated power to detect treatment group differences in linear change across all three assessments. Prior data indicated a main effect of treatment (EPIC versus enhanced group education) for linear change in HbA1c of 0.20, and between – and within – PACT variance in linear change of 0.018 and 0.206, respectively. These values indicate a small-to-medium between-groups effect size of 0.42. A total of 284 participants allows for 80% power to detect a slightly larger effect size ( $\delta = .53$ ) for repeated measures analyses of linear change over time. Furthermore, there is 98% power to detect a medium effect size of  $\delta = .75$ .

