#### **5.6.B. Data Collection Strategy § 5.1.H.**

#### **5.6.C. Data Analysis**

Specific Aim 1: H1 Analysis (Summative Evaluation). We will first calculate descriptive statistics such as frequencies, proportions, means, and standard deviations for reach, adoption, and implementation measures for the overall sample (i.e., VISN 12 and Houston) and for each specific facility. We will determine cost-utilization of resources within both study arms and the incremental cost-effectiveness ratio (ICER), which is the difference in the estimated mean cost between the intervention and control groups divided by the difference in the estimated mean effectiveness between the two study arms. The base-case will be the control group. We will estimate two ICERs: 1) the incremental cost per additional number of study patients with clinically significant HbA1C reductions, and 2) the incremental cost per additional quality adjusted life-year gained, of the intervention arm over the study period respectively. We will calculate ICER as a ratio of the difference in the estimated mean total cost between the EPIC and EUC groups divided by the difference in the estimated mean number of patients whose HbA1c levels are significantly improved between the two study arms. Similarly, we will calculate ICER of the intervention in terms of the quality adjusted life-year as a ratio of the difference in the estimated mean total cost between the intervention and control groups divided by the difference in the estimated mean total number of quality adjusted life-year between the two study arms. We will use a commonly used threshold, \$50,000 per quality adjusted life-year gained, as a reference point to determine if the intervention is cost effective.

Because cost data are typically right-skewed and also subject to bias due to death and/or attrition, we will directly model the logarithm of costs using generalized linear modeling with a logarithmic link function and inverse probability weight to adjust for these potential biases. We will control any baseline imbalance between groups with respect to the cluster and study population characteristics in the calculations of expected mean cost and effectiveness. The estimated value of cost and quality adjusted life-year will not be discounted given a relatively short follow-up period in the study.

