We will conduct exploratory analyses to examine associations between implementation measures (RE-AIM elements in table 5) and study outcomes following the conclusion of Phase 2. For example, for all eligible patients, within each PACT demographic characteristics will be compared between enrolled and non-enrolled patients using chi-square tests and independent samples t-tests. Fisher's Exact Test and the Wilcoxon Mann-Whitney tests will be used where appropriate. An index of reach representativeness will be calculated for each PACT which will then be correlated with post-intervention outcomes, controlling for respective baseline values. Similarly, for all PACTs sampled, PACT characteristics (e.g., panel size) will be compared between sampled and non-sampled PACTs using chi-square tests and independent samples t-tests. An index of adoption representativeness will be calculated for each PACT which will then be correlated with post-intervention outcomes, controlling for respective baseline values. Additionally, for patients receiving the EPIC intervention within each PACT, post-intervention HbA1c will be separately regressed on 1) the proportion of group sessions attended, 2) the proportion of individual sessions attended, and 3) baseline objective ratings of the group leader's fidelity. These models will control for baseline HbA1c and will be conducted using ANCOVA methods. Predictors that are significant at  $p < 0.25$  will be included in a multiple linear regression to examine both collective and unique predictors of post-intervention HbA1c levels (once again controlling for baseline HbA1c). Similar univariate and multivariate models will be formed to predict post-intervention DDS.

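### Reach is tested only within each PACT, at about 12 versus 15 patients; one PACT-stratified difference with a confidence interval would tell far more (minor)

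*Combined protocol and SAP*

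**What the plan says.** Table 5 (section 5.5.A) defines reach as "Representativeness of patients who are willing to participate in the intervention". Its measure compares enrolled participants from a PACT panel with all eligible patients on that panel. Section 5.5.A.i states the same comparison without naming a test.

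Section 5.6.C, Specific Aim 1, puts this into practice in three ways.

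- **Descriptive statistics** are planned "for reach, adoption, and implementation measures for the overall sample (i.e., VISN 12 and Houston) and for each specific facility".
- **Significance tests** are given as an example of the exploratory work: "within each PACT demographic characteristics will be compared between enrolled and non-enrolled patients using chi-square tests and independent samples t-tests". The small-sample alternatives follow: "Fisher's Exact Test and the Wilcoxon Mann-Whitney tests will be used where appropriate".
- **A per-PACT index** is planned: "An index of reach representativeness will be calculated for each PACT which will then be correlated with post-intervention outcomes". No formula is given.

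The stated purpose of the block that holds the tests and the index is: "We will conduct exploratory analyses to examine associations between implementation measures (RE-AIM elements in table 5) and study outcomes".

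Section 5.6.A supplies the sizes: "an average of 27 eligible patients per PACT, and expect that an average of 12 patients per PACT will participate", with 24 PACTs and 284 patients in total. No power, precision or interval is stated for the reach comparison anywhere.

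**The concern.** Representativeness is a statement of similarity. A difference test with no estimate or interval supports it only if the test could have detected a difference worth knowing about. Splitting the data by PACT cuts each test to a few dozen patients, so a non-significant result fits both good and poor representativeness in that PACT.

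At stake is how well the trial can describe whom it reached, which bears on how widely the effectiveness result applies. Reach is also one of the measures that define implementation in H1. The index matters too: if it were built from within-PACT p-values, its correlation with outcomes would rest largely on noise.

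**Working it through.** **Inputs.**
- Eligible per PACT 27, participating 12, PACTs 24, total N 284, design effect 1.2013 (section 5.6.A). Non-enrolled per PACT is derived: 27 − 12 = 15.
- Two-sided alpha 0.05, stated in section 5.6.A and assumed to apply to these exploratory tests.

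**The plan's own figure.** Deff = 1 + (12 − 1) × 0.0183 = 1.2013. Then 100 × 1.2013 ≈ 120 per arm, 120/0.85 = 141.2, rounded up to 142, so N = 284. 284/24 = 11.8 patients per PACT. The figure reproduces, and it confirms 12 enrolled per PACT as the plan's own average.

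**One PACT, 12 versus 15, continuous trait.** Noncentral t with df = 25, critical value 2.06, noncentrality d × √(12 × 15/27) = 2.582 d.

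| True difference | Power |
|---|---|
| 0.5 SD | 24% |
| 0.8 SD | 51% |
| 1.0 SD | 70% |
| 1.13 SD | 80% |

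**One PACT, binary trait (illustrative rates).** For 30% versus 50%, exact enumeration gives 20% power with the uncorrected chi-square test and 13% with Fisher's test.

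**One PACT, precision.** The SE of a standardized difference is about √(1/12 + 1/15) = 0.387. The 95% half-width is 1.96 × 0.387 = 0.76 SD (0.80 with the t quantile).

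**Sensitivity to the eligible count.** The screening figures suggest larger panels: 3,020/75 ≈ 40 or 3,776/75 ≈ 50 eligible per PACT. With 12 enrolled, power at 0.5 SD is 29% (12 versus 28) or 32% (12 versus 38).

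**The 24 tests as a set, one characteristic, treated as independent.**
- True 0.5-SD difference in every PACT: 24 × 0.237 = 5.7 significant PACTs expected; three or more in 95% of cases.
- No difference in any PACT: 24 × 0.05 = 1.2 expected; three or more in 12% of cases.

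**Same data in one stratified comparison.** Eligible 24 × 27 = 648; non-enrolled 648 − 284 = 364. SE ≈ √(1/284 + 1/364) = 0.079; half-width 1.96 × 0.079 ≈ 0.16 SD. Power is 88% at 0.25 SD and above 99.9% at 0.5 SD. If both counts are cut by the design effect (284/1.2013 = 236 and 364/1.2013 = 303), the half-width is still only about 0.17 SD.

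**The case against.** The strongest defence is that the plan nowhere makes the inferential mistake. A reader might infer that a non-significant within-PACT test will be taken as proof of representativeness, but no such rule is written. The tests are introduced as examples within exploratory work whose aim is to relate implementation measures to outcomes. Descriptive reach statistics, overall and by facility, let a reader see the size of crude differences. This stands. The fault is a missing estimate and an undefined index, not a stated wrong conclusion.

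A reader might also infer that the tests cannot tell representative from unrepresentative enrolment at all. That goes too far. Taken together, the 24 results for one characteristic do discriminate (5.7 versus 1.2 significant PACTs expected), and for a large difference of 0.8 SD a single PACT is about an even bet. But the plan specifies no way of combining the 24 results, and a count of significant tests is a poor substitute for an estimate.

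Table 5 does define reach panel by panel, and the planned correlation needs a PACT-level quantity. A stratified estimate respects that structure, and a PACT-level index can sit beside it.

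It is tempting to extend the point to adoption, where "PACT characteristics (e.g., panel size) will be compared between sampled and non-sampled PACTs using chi-square tests and independent samples t-tests". The documents do not support this: section 5.5.A.i asks which PACT characteristics differ, and a difference test fits that question.

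**Conclusion.** The point holds as a minor one. The only specified inferential reach comparison is a set of separate within-PACT tests, each with about 24% power for a 0.5-SD difference (32% with 50 eligible) and a half-width near 0.76 SD. Individually they say little about representativeness. No enrolled versus non-enrolled difference with an interval is planned, and the index has no formula. A stratified analysis of the same data narrows the half-width to about 0.16 SD, roughly a fivefold gain.

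This rests on the plan's averages of 27 and 12 per PACT, on 15 and 364 non-enrolled derived from them, and on alpha 0.05 applying to these tests. Panels of 40 to 50 eligible patients would not change the conclusion. The HbA1c and DDS comparisons are untouched.

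**What to change.** In section 5.6.C, Specific Aim 1:

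1. Make the main reach comparison one PACT-stratified estimate of enrolled versus non-enrolled eligible patients across all PACTs. For each characteristic, report the standardized difference, or the difference in proportions, with a 95% CI.
2. Give the formula for the per-PACT reach index, and build it from standardized differences, not p-values.
3. State that representativeness will not be inferred from a non-significant within-PACT test.

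A formal equivalence margin is optional; the documents supply no basis for a particular value.

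The cost is a few sentences of text and slightly more analysis work, with no new data collection. Per-PACT p-values would receive less emphasis.

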#### **5.5.B. Data Collection Strategy § 5.1.H.**

#### **5.5.C. Study Variables § 5.1.I.**

### **5.6 Data Analysis**

#### **5.6.A. Sample Size Calculation/Sample size determination**

Sample size is calculated according to the estimated intervention effect size at post-intervention. We then estimate power to detect treatment effects at the post-maintenance (10-month) follow-up as well as power to detect treatment differences in linear change across the three time points for a 3-level cluster-randomized trial with repeated assessments. We will adjust models for baseline covariates of study patients. All tests will be two-sided with an alpha of 0.05. In our recent RCT, differences in HbA1c change between EPIC versus enhanced group education indicated medium treatment effects at post-treatment and at 1-year (Cohen's  $d = 0.48$  and  $0.42$ , respectively). A similar trial revealed a treatment difference between a glucose self-monitoring protocol and an active control group in DDS scores that correspond to large effects of treatment at 1-year (all pre-post  $d$ s  $> 0.80$ ). To capture treatment effects for both clinical and patient centered outcomes in this implementation trial, a conservative small-to-medium effect size of  $d = 0.40$  (which is 16.67% smaller than the effect found for HbA1c in the prior trial) was used to calculate sample size. Assuming no intra-class correlation (ICC) within

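### The p < 0.25 screen before the exploratory implementation regression miscalibrates a joint test of the surviving predictors: read at 0.05, it rejects in about 8% to 14% of null trials

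*Combined protocol and SAP*

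**What the plan says.** The analysis is introduced as exploratory: "We will conduct exploratory analyses to examine associations between implementation measures" and study outcomes (section 5.6.C, Specific Aim 1). It concerns the intervention arm only, "for patients receiving the EPIC intervention within each PACT". Post-intervention HbA1c is "separately regressed on 1) the proportion of group sessions attended, 2) the proportion of individual sessions attended, and 3) baseline objective ratings"; the third item refers to how faithfully group leaders delivered the sessions. On adjustment: "These models will control for baseline HbA1c and will be conducted using ANCOVA methods".

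The second stage follows at once. The entry rule reads: "Predictors that are significant at $p < 0.25$ will be included". As to the purpose of the second model, which again adjusts for baseline HbA1c, the plan says that the survivors "will be included in a multiple linear regression to examine both collective and unique predictors of post-intervention HbA1c levels". For the second outcome, the rule is: "Similar univariate and multivariate models will be formed to predict post-intervention DDS".

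The plan gives no significance level specific to these models. The only general statement is in section 5.6.A: "All tests will be two-sided with an alpha of 0.05". The documents provide no selection-adjusted p-value, no resampling that repeats the screen, no hold-out sample and no full model fixed in advance.

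**The concern.** A joint test at 0.05 has its nominal error rate when the predictors are chosen without looking at the outcome. Here a predictor enters because it was associated with that outcome in those patients. Survivors therefore tend to look jointly predictive even when none of the three measures matters.

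The screen also works against separating the three contributions. Group and individual attendance are likely to be correlated. If one narrowly fails the screen, the other's coefficient is reported as a unique contribution without adjustment for it.

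What is at stake is over-reading of which implementation features go with better HbA1c or DDS. The trial's effectiveness comparison is not at stake.

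**Working it through.** **Inputs from the documents.** Three candidates, a screen at p < 0.25, baseline outcome in every model, EPIC arm only (5.6.C); 142 patients per arm, up to 15% attrition, two-sided 0.05 (5.6.A).

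**Reproducing the plan's sample size.** For d = 0.40 and 80% power the normal formula gives 99 per arm (plan: 100, with power 80.7%). The design effect is 1 + 11 × 0.0183 = 1.2013, so 100 × 1.2013 = 120. Dividing by 0.85 gives 142. The plan's figure is reproduced. EPIC patients with outcome data: 142 × 0.85 ≈ 121. The plan states no error rate for the screened regression.

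**Assumptions.** *Collective* prediction is judged by the joint F test of the survivors given baseline, at 0.05. If nothing survives, that counts as no rejection. The model is pooled over the EPIC arm: with 24 PACTs there would be only 142/24 ≈ 6 EPIC patients per PACT, too few for a separate regression in each. The correlation r between the two attendance proportions is not in the documents, so a range is shown.

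**Hand check, three independent null predictors.**
- Exactly one survives: 3 × 0.25 × 0.75² = 0.4219. Its p-value is then uniform on (0, 0.25), so it rejects with probability 0.05/0.25 = 0.20. Contribution: 0.4219 × 0.20 = 0.084.
- Two survive: 3 × 0.25² × 0.75 = 0.1406. The joint test rejects in 0.365 of these (large-sample calculation, 4 million draws). Contribution: 0.051.
- Three survive: 0.25³ = 0.0156, rejecting in 0.540. Contribution: 0.008.
- Total: 0.084 + 0.051 + 0.008 ≈ 0.144.

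The one-survivor path alone already exceeds 5%.

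**Simulation, 40,000 null trials per setting** (fidelity uncorrelated with attendance):

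| r | Screened, n = 120 | Screened, n = 142 | All three, no screen, n = 120 | Final model formed, n = 120 | Rejects given formed, n = 120 |
|---|---|---|---|---|---|
| 0 | 14.2% | 14.8% | 4.9% | 57.9% | 24.6% |
| 0.3 | 13.4% | 13.3% | 4.9% | 57.0% | 23.4% |
| 0.5 | 12.0% | 11.7% | 5.0% | 55.9% | 21.5% |
| 0.8 | 8.8% | 8.7% | 5.2% | 51.9% | 17.0% |
| 0.9 | 8.0% | 7.9% | 4.9% | 49.4% | 16.1% |
| 0.95 | 7.7% | 7.5% | 5.1% | 47.8% | 16.2% |

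A separate run at n = 121 gave 14.6%, 11.9%, 9.7% and 8.1% at r = 0, 0.5, 0.7 and 0.9. With fidelity shared within 12 assumed leaders and r = 0.8, the screened rate was 8.5% and the unscreened rate 5.1%. Clustering of the outcome was not simulated.

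**Unique prediction.** Counting all null trials, each predictor is declared significant in the final model in 2.1% to 5.2% of them, so the screen does not inflate these tests. The omitted partner is a separate matter. In null runs where group attendance passed the screen, individual attendance failed it 49% of the time at r = 0.7 and 29% at r = 0.9.

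**The case against.** The strongest reply is that the plan commits to less than is being tested. It calls the analysis exploratory, names no F test, sets no level for this model, and gives no rule for declaring the predictors jointly predictive. A liberal screen is a familiar hypothesis-generating step, and a purely descriptive report would claim no error rate. This stands as a limit on consequence, and the 0.05 joint test is indeed an inference from section 5.6.A. It does not remove the problem. The model's stated purpose is to examine collective prediction, and the ordinary output for that is a joint p-value that the screen has made too small.

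Four stronger readings are tempting but not supported:
- *The error rate is three to five times nominal.* The 16% to 25% behind that holds only when a final model is formed. Over all null trials the rate is about 8% to 14%.
- *14% is the expected figure.* It needs uncorrelated attendance. Sections 5.1.E.iii and 5.1.F.iii pair an individual session with each of the six group sessions, so a substantial correlation is more plausible.
- *The single-predictor conclusions are also inflated.* They are not. The one defect there is the missing adjustment for a dropped partner, and all three one-predictor models are still run.
- *The trial's conclusions rest on this.* H1 links formative PARIHS measures to implementation, and H2 and H3 have their own ANCOVA models (5.6.C.i and 5.6.C.ii). None depends on this regression.

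It is also fair that the simulation is simpler than the trial. Fidelity is a leader-level rating, and patients are treated in groups of 5 to 8 (5.1.E.iii).

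**Conclusion.** The point holds as a minor one. Screening at p < 0.25 on the same outcome and patients makes a joint test of the survivors miscalibrated. With a joint F test at two-sided 0.05, the overall null rejection rate is about 14% with uncorrelated attendance and about 8% to 10% at assumed correlations of 0.7 to 0.9. It was above 5% in every setting tried. The model with all three predictors and no screen gives about 5%.

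These figures rest on the inferred test, a pooled EPIC-arm model, independent patients and an assumed attendance correlation. The consequence is confined to over-reading exploratory implementation predictors of HbA1c and DDS.

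**What to change.** In section 5.6.C, delete the p < 0.25 screen. For each of HbA1c and DDS, pre-specify one model, pooled over EPIC patients, with the baseline outcome and all three implementation measures, accounting for clustering by group or leader where present. Name the joint test of the three measures as the assessment of collective prediction, and report partial estimates with 95% confidence intervals for unique prediction. Keep the one-predictor models as descriptive.

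If the screen is kept, either calibrate the joint p-value by a permutation that repeats the screen, or report the model descriptively without a joint p-value.

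The cost is a sentence or two of wording and no new data. The model spends two extra degrees of freedom if one predictor would have survived and three if none would, which about 120 patients can bear. Intervals for the two attendance terms will be wider if they are highly correlated, which reflects what the data can separate. The change does not address multiplicity across the three partial coefficients: at least one is nominally significant in roughly 11% to 15% of null trials under the full model. They should be read as estimates.
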